Clinical Investigation Protocol (incl. statistical considerations)

Clinical examination of the F-Composite 2 Systems in the direct filling therapy

(NCT03221660)

INDEX

1. OBJECTIVES AND HYPOTHESES OF THE CLINICAL INVESTIGATION	3
2. GENERAL OVERVIEW OF THE CLINICAL INVESTIGATION	4
3. JUSTIFICATION FOR THE STRUCTURE OF THE CLINICAL INVESTIGATION.....	4
4. INVESTIGATORS	5
5. MATERIALS	5
6. RISKS AND BENEFITS OF THE INVESTIGATIONAL PRODUCT AND THE CLINICAL INVESTIGATION	6
7. STRUCTURE OF THE CLINICAL INVESTIGATION.....	7
7.1 GENERAL INFORMATION	7
7.2 PRODUCTS AND REFERENCE PRODUCTS	8
7.3 PARTICIPANTS (IN-/EXCLUSION CRITERIA).....	9
7.4 TREATMENTS	10
7.5 SPECIFICATIONS FOR MONITORING	11
8. STATISTICAL CONSIDERATIONS	12
9. DATA MANAGEMENT.....	12
10. CHANGES TO THE CLINICAL INVESTIGATION PROTOCOL	13
11. DEVIATIONS FROM THE CLINICAL INVESTIGATION PROTOCOL.....	13
12. PROOF OF USE OF THE PRODUCT.....	13
13. DECLARATION OF CONFORMITY	13
14. PROCEDURE FOR OBTAINING CONSENT	14
15. ADVERSE EVENTS, ADVERSE EFFECTS OF THE PRODUCT AND PRODUCT DEFECTS..	14
16. POPULATION THAT CAN BE PRESSURED	14
17. PREMATURE TERMINATION OR SUSPENSION OF THE EXAMINATION	15
18. PUBLICATION POLICY	15
19. REFERENCES	15

1. Objectives and hypotheses of the clinical investigation

a) The aim of this prospective study is to evaluate the clinical performance of F-Composite 2, a proven flowable bulk material and adhesive system for the restoration of masticatory posterior fillings (Class I and II), all three materials being polymerized with Bluephase PowerCure (flash mode).

b) Primary hypotheses to be accepted or rejected by statistical data from the clinical investigation.

[name]. [name] from the Biostatistical Department of the Institute of Social and Preventive Medicine at the University of Lausanne, Switzerland, has performed a case number calculation. Assuming that a maximum of 10% post-operative hypersensitivity is acceptable, but actually only 5% is expected, the following formula can be used to calculate the case number (80% power, using a chi-square test at 5% probability of error)

$$N = (1.96 * \sqrt{0.95 * 0.05} + 0.84 * \sqrt{1 * 0})^2 / (1 - 0.95)^2 = 73 \text{ participants or fillings}$$

Furthermore, if one assumes - based on internal experience - that after one year there is a drop-out rate of 2%, 75 fillings are necessary at the beginning of the study to statistically confirm the primary endpoint (post-operative hypersensitivities).

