(c) claimed and intended performance of the test product, which shall be demonstrated.

The following working hypotheses should be clarified:

- Teeth restored with the F-Composite 2 system have postoperative hypersensitivity in a maximum of 10% of cases after 1 month.
- A maximum of one tooth shows a loss of vitality within 12 months.
- With the selected application protocol, the F-Composite 2 system enables a filling quality at least comparable to F-Composite (see study "Clinical investigation of Flash Composite in direct restorative therapy" CEC-ZH No. 2011-0150/5.) After 2 years a maximum of 3 fillings should be replaced due to poor quality.

(d) The following risks shall be assessed:

- post-op discomfort. In almost all clinical studies with direct filling materials, postoperative hypersensitivity occurs in the range of a few percent of the treated teeth. Whether the probability of occurrence is increased when using the F-Composite 2 restorative system can only be estimated by a clinical study.

- Inflammation/death of the pulp (the "dental nerve"). In December 2015 a clinical study was completed after an observation period of three years (KEK-ZH No. 2011-0150/5), in which the filling material was polymerized with 10 000 mW/cm² for one second, but without exposing the adhesive to this light intensity. No permanent damage to the pulp due to the high light intensity or temperature gradient was observed. In addition, Bluephase PowerCure was used to investigate the temperature gradient in the pulp in in vitro studies on extracted teeth. The absolute temperature was comparable to other lamps (recorded in investigator's brochure). However, the temperature gradient was steeper.

- Cracks in the tooth structure or between tooth and restoration or marginal gaps which could lead to discoloration, secondary caries, filling fracture, filling loss or tooth fracture. In very severely hollowed cavities on extracted molar teeth with undercuts (worst-case scenario) under the cusps, horizontal cracks in the tooth structure could be observed in vitro in bulk fillings with the flowable composite (recorded in validation report examiner brochure). For this reason, special attention is also paid to this point during the clinical investigation.

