- Unexpected changes in the filling surface that could lead to roughness, discolouration or increased wear of the material. As the material is similarly polishable as a conventional composite material, it is expected that no more surface discolouration will be observed.

2. General overview of the clinical investigation

The F-Composite 2 system is a coordinated system of filling materials, adhesive and polymerization unit for direct restorative therapy in dentistry.

The aim of this single-arm prospective clinical study is to investigate the F-Composite 2 system in direct filling therapy of class I and II cavities.

The following working hypotheses should be clarified:

- Teeth restored with the F-Composite 2 system have postoperative hypersensitivity in a maximum of 10% of cases after 1 month, which corresponds to a frequency as described in the literature.
- With the selected application protocol, the F-Composite 2 system enables at least comparable restorative quality to F-Composite (see study "Clinical investigation of Flash Composite in direct restorative therapy" CEC-ZH No. 2011-0150/5.) After 2 years a maximum of 3 fillings should be replaced due to poor quality.
- The rate of loss of vitality after 1 year is maximum 1%, which corresponds to a frequency as described in the literature.

The clinical investigation will be conducted with a maximum of 75 patients. No more than two restorations will be placed in any one patient. For inclusion and exclusion criteria, see item "7.3 Participants".

Recalls take place after 6, 12, 24, 60 months.

Aftercare

At the end of the study period or when patients leave the study, they will continue to be routinely cared for by their private dentist.

3. Justification for the structure of the clinical investigation

In summary, it can be concluded from the literature cited in the investigator's brochure that restorative composites are suitable for the intended indications and show a clinically acceptable performance.

Up to now, polymerization of the adhesive or a composite increment takes 5 to 40 seconds, depending on the material used and the polymerization lamp used to cure the material. Currently, the upper limit of available light intensities for direct restorations is approximately 2'000 mW/cm². In a recent study from Norway (Kopperud et. al, 2017), in which 740 dentists from the public sector were interviewed, it was shown that these dentists exposed each composite increment for an average of 27 s.

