7.4 Treatments

a) Description of all treatments administered to the investigation participants during the clinical investigation Three operators place 25 fillings each.

Preparatory measures and cavity preparation

- A medical and dental anamnesis and detailed findings are taken for each patient and, if necessary, x-rays are taken. A visual analogue scale is used to record the preoperative complaints of the tooth to be restored with regard to temperature stimulus and bite sensitivity. However, no cold or bite sensation is set for this purpose. The vitality is checked with a cold spray. In addition, a therapy plan is drawn up in accordance with the restoration concept.
- A digital photo of the initial state is taken. The vestibular and oral views are printed out. The occurrence and extent of horizontal tears are drawn on it.
- If possible, rubber dams are used for drainage. If a rubber dam is not possible, an appropriate relative draining method is used (OptraGate, cotton rolls, saliva ejector).
- Then the insufficient filling or caries is removed.
- The preparations are done with 80 µm diamonds, a finish of the cavity edges with 25 µm diamonds. The cavity edges in the enamel are chamfered, but not gingivocervically.

Measurement of the cavity and renewed documentation of melt cracks

- A digital photo of the prepared cavity is taken
- The lowest point of the respective proximal boxes and occlusal pull-through is measured with a PA probe (Hu-Friedy PCPUNC 15) and documented on the CRF I. The reference for the proximal box is the proximal-occlusal cavity margin in the marginal ridge area and, for determining the occlusal pull-through depth, the occlusal cavity margin adjacent to the lowest point. The determination should be made with an accuracy of ± 1 mm.
- The average width of the cavity is given in absolute terms (accuracy ± 1 mm). The already mentioned periodontal probe is also used as an aid here.

- Prior to conditioning, the tooth is again examined for horizontal enamel cracks, which are recorded in the printed photographs in terms of their extent and localization and recorded on the CRF I. A cold-light fibre optic (light probe by Lercher) is used as an aid.
- The residual dentin thickness above the pulp is determined with a prepometer at the site with the lowest layer thickness (Wegehaupt et al. (2009)).

The partial matrix system from Garrison (Compositight) or Triodent (V3) is used as the matrix.

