7.5 Specifications for monitoring

This clinical investigation will be monitored by the sponsor at defined timely intervals. The Monitoring Plan lists the activities within the scope of monitoring.

8. Statistical considerations

- a) Due to the study design, no special statistical methods are necessary.
- b) The sample size is 75 fillings
- c) validity of the clinical investigation: the system is suitable for the market if the acceptance criteria are met.
- d) Expected drop-out rate: Analysis of older comparable studies show that an annual drop-out rate of 2% can be expected. Accordingly, three fillings could no longer be checked after 2 years.
- e) Acceptance criterion for post-operative hypersensitivity after 4 weeks: $\leq 10\%$ (=6 fillings).
Acceptance criterion for loss of vitality after 1 year: maximum 1 restored tooth
Acceptance criterion for filling replacement after 2 years: maximum 3 fillings
- g) If more than 50% of the patients suffer from postoperative hypersensitivity after placing at least 20 fillings, the study would be terminated.
- k) If patients discontinue the study or drop out for other reasons (including extraction of the tooth from a cause not related to the study, change of the opposing dentition or treatment by an external dentist), they are considered a drop-out and are reported separately with the drop-out cause (CRF V).
The recall data obtained up to the time of withdrawal from the study are used in the evaluation.

9. Data management

- a) Data verification is carried out with plausibility checks. The data is encrypted, since the patient names do not appear in the data tables, but the cases can be assigned using case numbers and patient IDs.
- c) The archiving of the data takes place on the company's secure servers. The data is stored as SPSS data sheets in anonymized form. The traceability is given by case numbers.
- d) The retention period of the data after completion of the study is 10 years.

Since all persons involved in the study, especially the operators and the evaluator, are familiar with and apply the company's internal guidelines regarding "Good Documentation Practice" (SOP-00081-EN; Good Documentation Practice), the traceability of changes is ensured by the dating and sizing of corrections.

CRFs, radiographs and clinical images will be collected as source data in this study.

Authorities and the Monitor will be granted access to the original data at any time, should this be necessary.

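### At conventional 95% confidence, 75 fillings cannot confirm the section 2 hypothesis that 1-year vitality loss is at most 1%; meeting the one-tooth rule supports an observed count only

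*Combined protocol and SAP*

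**What the plan says.** The vitality hypothesis appears in two forms. Section 2 gives it as a rate with an outside benchmark: "The rate of loss of vitality after 1 year is maximum 1%, which corresponds to a frequency as described in the literature". Section 1 c), under a lead-in describing performance that the investigation is meant to demonstrate, gives it as a count: "A maximum of one tooth shows a loss of vitality within 12 months". Section 8 e) also uses a count: "Acceptance criterion for loss of vitality after 1 year: maximum 1 restored tooth". Section 8 c) then ties suitability for the market to meeting the acceptance criteria, of which this is one.

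Section 7.1 c) makes devitalization a secondary endpoint, and section 7.1 a) confirms that there is no control group. Section 8 b) states "The sample size is 75 fillings", consistent with section 7.4: "Three operators place 25 fillings each". The sizing argument in section 1 b) concerns hypersensitivity only: "Assuming that a maximum of 10% post-operative hypersensitivity is acceptable, but actually only 5% is expected", with "80% power, using a chi-square test at 5% probability of error". For vitality loss the plan gives no test, interval or statement of precision. Section 8 a) says: "Due to the study design, no special statistical methods are necessary".

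**The concern.** A hypothesis about a rate is judged by a count of zero or one in a sample chosen for a different and much more frequent event. With so few teeth, a count of zero or one is compatible with rates several times the stated 1%.

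Pulp inflammation and pulp death are among the risks that section 1 d) sets out to assess, and the same section reports a steeper temperature gradient in vitro with the new lamp. With no concurrent control, any statement about vitality loss relative to the literature rests on this one count. If the criterion is met, the section 2 wording invites the conclusion that the true rate is at most 1%, and the data could not carry that conclusion.

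**Working it through.** **Inputs.** Claimed rate 1% (section 2). Rule: at most one loss (sections 1 c and 8 e). n = 75 fillings (section 8 b; 3 × 25 in section 7.4). Drop-out 2% per year (section 8 d), so 75 × 0.98 = 73.5, or 73 to 74 fillings evaluable at 12 months. Confidence level 95%: assumed, by analogy with the 5% error that section 1 b) sets for hypersensitivity. Fillings are treated as independent.

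**Step 1: the plan's own figure.** The formula printed in section 1 b) gives (1.96 × √(0.95 × 0.05) + 0)² / 0.05² = 72.99, rounded up to 73. Then 73 / 0.98 = 74.5, rounded up to 75. The printed number reproduces from the printed formula, and no vitality rate enters it.

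**Step 2: exact (Clopper-Pearson) upper limits.** For zero losses, solve (1 − p)ⁿ = α, so p = 1 − α^(1/n). For one loss, solve (1 − p)ⁿ + n·p·(1 − p)ⁿ⁻¹ = α. Use α = 0.05 for the one-sided limit and α = 0.025 for the two-sided limit.

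| Losses / evaluable | Observed | Upper limit, one-sided 95% | Upper limit, two-sided 95% |
|---|---|---|---|
| 0/75 | 0% | 3.9% | 4.8% |
| 1/75 | 1.3% | 6.2% | 7.2% |
| 0/73 | 0% | 4.0% | 4.9% |
| 1/73 | 1.4% | 6.3% | 7.4% |

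For example, 1 − 0.05^(1/75) = 0.039 and 1 − 0.025^(1/75) = 0.048. Other two-sided intervals for 0/75 also reach well past 1%: Wilson 4.9%, Jeffreys 3.3%.

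**Step 3: the same point without choosing a confidence level.** If the true rate were exactly 1%, zero losses in 75 would occur with probability 0.99⁷⁵ = 0.47. The best possible result therefore bounds the rate at 1% with only 1 − 0.47 = 53% one-sided confidence.

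**Step 4: how often the rule is met.** P(pass) = (1 − p)⁷⁵ + 75·p·(1 − p)⁷⁴.

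- p = 1%: 0.471 + 0.357 = 0.83
- p = 2%: 0.220 + 0.336 = 0.56
- p = 3%: 0.102 + 0.236 = 0.34

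With 73 evaluable the values are 0.83, 0.57 and 0.35.

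**Step 5: scale.** For zero losses to bring the upper limit down to 1%, n must satisfy 0.99ⁿ ≤ α. One-sided: ln 0.05 / ln 0.99 = 298.1, so 299 fillings. Two-sided: 368. Even two fillings in each of 75 patients, 150 in all with no loss, would leave 2.0% one-sided or 2.4% two-sided. These figures show the size of the gap; they are not a proposed sample size.

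**The case against.** The strongest reply is that vitality loss is a secondary endpoint with a descriptive criterion. Sizing a trial on its primary endpoint is ordinary practice. The plan promises no test or confidence level for this count, and two of its three statements are already counts. All of that stands, and it rules out several stronger readings.

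- A reader might infer that no possible result could support the 1% figure in any sense. The documents do not bear this out. Read descriptively, 0/75 is compatible with a rate of at most 1%. What fails is confirmation at 95%, a level borrowed from the hypersensitivity calculation.
- A reader might infer that section 8 plans to conclude equivalence with the literature. It does not: section 8 c) refers only to the acceptance criteria. The literature clause is in section 2, where it may simply explain the origin of the 1%; the same clause follows the 10% hypersensitivity figure.
- A reader might infer that the rule is too strict because it fails a system at exactly 1% about 17% of the time. The hypothesis covers all rates up to 1%, and at 0.5% the rule is passed with probability 94.5%.
- A reader might infer that the trial must be enlarged. Nothing in the plan requires this secondary endpoint to be powered.

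The reply does not dispose of the section 2 bullet. That bullet is worded as a rate, section 1 c) presents the parallel hypotheses as performance to be demonstrated, and section 8 c) attaches a market decision to the criterion. If only a descriptive count is intended, the text should say so.

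**Conclusion.** The point holds in limited form. The rule in section 8 e) can deliver an observed count, but it cannot confirm the section 2 rate at conventional confidence. Even a perfect result leaves rates up to 3.9% one-sided or 4.8% two-sided unexcluded, and the one loss that the rule permits leaves 6.2% or 7.2%. Without any appeal to a confidence level, a system at twice the stated rate would still pass slightly more often than not (56%).

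The limits rest on the assumed 95% level, on 73 to 75 evaluable fillings and on independence between fillings. Section 2 allows two restorations in a patient, and positive correlation within patients would widen the limits. The source of the 1% cannot be checked from the documents and is taken as stated.

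This is separate from the mismatch between 1% and one tooth in 75 (1.33%). Reconciling those two figures alone would leave the point standing, because zero losses does not confirm 1% either.

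**What to change.** - **Section 2.** Reword the vitality bullet as an observed count, matching sections 1 c) and 8 e), and add that the study does not establish a true rate of 1% or below.
- **Section 8 e).** Report vitality loss with its exact two-sided 95% confidence interval, using the number of teeth evaluable at 12 months as the denominator. A fixed upper limit computed at 75 should not be written in, since drop-out will change it. Beside the criterion, give the pass probabilities: 83% at a true 1%, 56% at 2% and 34% at 3%, stating that they assume 75 evaluable fillings.
- **Section 8 c).** Add one sentence: meeting the vitality criterion does not show that the rate is no higher than in the literature.

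Section 1 c) needs no change, nothing in section 8 c) needs deleting, and neither the acceptance criterion nor the sample size is altered. The cost is a few sentences and one interval. The downside is that the claim available to the sponsor becomes weaker.

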7.1 General information

a) It is a single-arm clinical investigation without a control or comparison group. This design was chosen because clinical studies ("Clinical investigation of Flash Composite in direct restorative therapy" CEC-ZH No. 2011-0150/5; "Clinical investigation of AdheSE One F Upgrade in direct restorative therapy" CEC-ZH_NR. 2012-0076) with direct fillings have already been conducted by the same dentists in the same institution. Accordingly, existing data regarding the quality of fillings can be used for comparison purposes. The chosen study design allows higher case numbers, which seems reasonable in view of the primary endpoint.

b) An investigator-blinding is carried out during the evaluation of the fillings during recall: the examiner does not know who placed the fillings. All follow-up examinations and the baseline findings are performed by an experienced evaluator.

c) Primary endpoint: postoperative hypersensitivity

Secondary end points: devitalization and therefore necessary endodontic treatment, quality of filling and therefore necessary replacement of fillings

d) The following assessment criteria shall apply:

Baseline Findings

The participants are recalled 7-10 days after placing the filling to record the baseline findings. In addition to the clinical examination, the participants are also questioned regarding sensitivity

to temperature and occlusion. The aesthetic integration of the filling is evaluated, the occlusion is checked and corrected if necessary. Photos of the restoration are also taken. For the baseline findings and for all recalls, the restorations are examined and evaluated (SQUACE and FDI criteria) using a special evaluation sheet.

On the findings sheet, the patient has to draw the sensitivity of the tooth in everyday life regarding temperature and bite sensitivity on an unscaled straight line of 10 cm. The distance from the left edge (zero point = no discomfort or pain) is measured to within 1 mm in the evaluation.

In the semi-quantitative evaluation of the fillings (SQUACE=SemiQUantitative Clinical Evaluation), the following findings are documented: secondary caries FDI 12, marginal gap FDI 6.b, marginal deficits FDI 6.c, marginal discoloration FDI 2.b and marginal fracture FDI 6.a (in each case as a percentage of the total margin)

The following FDI criteria are assessed using the FDI rating system

- Postoperative hypersensitivity or tooth vitality FDI 11
- Surface gloss FDI 1
- Surface discoloration FDI 2a
- Colour match and translucency FDI 3
- Fracture of material and filling retention FDI 5
- Proximal contact point FDI 8
- Patient satisfaction FDI 10
- Tooth integrity (tooth cracks and fractures) FDI 13

Based on the FDI System for Clinical Evaluation of Restorations (Hickel et al 2007, 2010), evaluations are assigned for each FDI criterion according to the following scheme

1= clinically ideal

2= clinically good

3= clinically acceptable

4= no longer clinically acceptable (but repairable)

5= clinically unacceptable, restoration must be replaced (repair not possible or not practical)

Horizontal cracks are plotted on the printout of oral or vestibular photographs of the tooth (before and after the filling is placed or during recall) and compared with the preoperative findings.

Follow-up examinations

Recalls take place after 6, 12, 24, 60 months. The restorations are evaluated according to the above criteria.

Photos are taken of all restorations at the examination appointments. If a patient suffers from postoperative complaints, the patient is examined again 14-20 or 30-35 days after the filling has been placed.

e) No special test equipment is used for the assessment of the test variables.

f) instructions for the exchange of participants are not required and no exchange takes place

